### 5.3 Primary Analytic Method for Objective 2 Primary Effectiveness Outcome Measure

Our primary outcome for the main Objective 2 (effectiveness) outcome is a patient-level measure of the number of days of acute care utilization over the follow-up period, which is a 2-year period for 5 of the 6 HCSs, and a 1.5-year period for the 6th HCS.

The primary analysis will be among individuals with an eligible PC visit pre-randomization who had an OUD diagnosis during the pre-randomization period (see definition of “Objective 2 primary study sample” in Section 3). The patient-level analysis will follow ITT principles, with patients analyzed according to the randomization group of the clinic to which they were assigned pre-randomization, regardless of the degree to which the clinic actually implemented the intervention, and regardless of whether the patient was actually treated by the NCM or seen post randomization.

We hypothesize that, among patients who had an eligible PC visit and were identified as having an OUD diagnosis pre-randomization (documented in their EHRs up to 3 years prior to randomization), individuals from a PROUD intervention clinic will have decreased acute care utilization after randomization as compared to individuals from a UPC clinic. We plan to fit a mixed-effect Poisson regression model (with log link) at the patient level to the number of days of acute care utilization. The model will account for clustering of patients within a clinic by including clinic-specific random intercepts. Specifically, the regression model will be of the following form:

$$\log[E(y_{ijk})] = \log(\text{days}_j) + \alpha + \beta * trt_{ij} + \gamma * z_{ijk} + \theta_{ij}$$

where

- $y_{ijk}$  is the observed number of days of acute care utilization of patient  $k$  in clinic  $i$  of HCS  $j$  over the follow-up period
- $trt_{ij}$  is the treatment indicator (PROUD intervention) for clinic  $i$  in HCS  $j$
- $z_{ijk}$  is the baseline value of the outcome during the two years prior to randomization for patient  $k$  in clinic  $i$  of HCS  $j$  ( $\gamma$  is the corresponding coefficient)
- $\theta_{ij}$  is the random effect for clinic  $i$  in HCS  $j$

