Because one of the HCSs was randomized at a later date than the others, not all HCSs have the same amount of follow-up time. To account for this difference, we will include in the model an offset term for the number of days of potential follow-up time (e.g., 2 years for 5 of the HCSs and 1.5 years for the 6th HCS); in the above model,  $\log(\text{days}_j)$  denotes the offset term where  $\text{days}_j$  denotes the days of follow up in HCS  $j$ .

We will evaluate our primary Objective 2 hypothesis by testing the null hypothesis  $H_0: \beta = 0$  versus the two-sided alternative hypothesis that  $\beta$  is non-zero with a type 1 error rate of 0.05. In cluster-randomized trials with a small number of clusters, a small-sample correction is often necessary to obtain correct type 1 error rates. Although small-sample degree of freedom (DF) correction methods have been evaluated for continuous and binary outcomes under generalized linear mixed-effect models (GLMMs), there has not been prior guidance of which approach to use in our setting with a count outcome and covariate adjustment. Given this lack of knowledge, members of the PROUD statistical team are conducting simulations to evaluate alternate small-sample DF methods in this setting. Our results so far suggest that the optimal choice of testing procedure varies depending on the data-generating scenario in terms of the intraclass correlation

coefficient (ICC), number of clusters, and sample size within a cluster; however, using the likelihood ratio test with the Between-Within (BW) DF correction method (also referred to as “inner-outer” approach) appears to perform generally well in the scenario that aligned most closely with PROUD Phase 1 data used in the power simulation (see Appendix C).

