#### **5.5.1 Rationale for Conducting Analyses Within a Secondary Sample**

It is expected that some of the patients who initiate treatment in PROUD intervention clinics will have been diagnosed with OUDs after randomization, potentially due to the PROUD intervention. It is also possible that patients may be newly attracted to the clinic (or to the health system entirely) potentially because of the PROUD intervention (based on the fact that at least 77% of patients treated in MA were new to the clinic after implementation). The primary analysis of Objective 2 described above would miss any impact of the PROUD intervention on both of these subsamples of patients, because they were not identified pre-randomization (because they were not previously diagnosed with OUDs or because they did not visit the clinic in the pre-randomization period). These secondary analyses within the secondary Objective 2 study sample, which includes patients seen in the trial clinics with an OUD diagnosis post-randomization only, are designed to capture these additional patients who may be affected by the PROUD intervention.

On the other hand, these secondary analyses must account for the fact that patients with newly recognized OUD in the PROUD intervention clinics post-randomization are likely to differ markedly from patients with newly recognized OUD in the UPC clinics post-randomization. Further, it is likely that these patients could differ in ways that may be associated with acute care utilization (e.g., patients could be referred for ongoing buprenorphine treatment from an ED or hospital that started treatment). To address this, analyses will adjust for covariates known or hypothesized to be associated with acute care utilization (based on prior literature), as well as secondarily for any additional covariate observed to differ across patients with newly recognized OUD post-randomization in the UPC versus PROUD intervention clinics.

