### **5.5.3 Primary Objective 2 Outcome Analysis within the Secondary Sample**

We plan to fit a similar mixed-effect Poisson regression model as in the primary Objective 2 analysis but that (1) includes additional covariates and (2) that allows the treatment effect comparing the PROUD intervention clinics to UPC clinics to differ among patients with newly

recognized OUD in the clinics post-randomization vs. those with visits to the trial clinics and OUD documented pre-randomization. Specifically, the model will be of the following form:

$$\log[E(y_{ijk})] = \log(\text{days}_i) + \alpha_0 + \alpha_1 \text{period}_{ijk} + (\beta_0 + \beta_1 * \text{period}_{ijk}) * \text{trt}_{ij} + \gamma * z_{ijk} + \theta_{ij}$$

where *period* is an indicator for the period when the patient was first recognized with OUD in the trial clinics (i.e., whether the patient is in the post-randomization sample or pre-randomization sample; see Section 3.3), and the other terms are defined as in the primary analysis, except for the covariate vector (*z*), which includes the set of covariates listed above in Section 5.5.2.

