We will evaluate our secondary Objective 2 hypothesis by testing the composite null hypothesis  $H_0: \beta_0 = \beta_1 = 0$  versus the alternative hypothesis that at least one of  $\beta_0$  or  $\beta_1$  is non-zero by conducting a likelihood ratio test. Additionally, we will estimate the treatment effect separately among patients identified in the pre-randomization period ( $\beta_0$ ) and patients identified in the post-randomization period ( $\beta_0 + \beta_1$ ). The coefficient  $\beta_1$  is the difference in the treatment effect comparing patients identified post-randomization to those identified in the pre-randomization period. This could either reflect a true difference in the treatment effect, or, more likely, it could reflect unmeasured confounders (not included in *z*) that differ between patients newly recognized with OUD post-randomization in the intervention versus UPC trial clinics. We do not have a specific hypothesis regarding  $\beta_1$  because new patients may be attracted to the clinic to receive the PROUD intervention, as seen in [name], and these patients may be sicker (or healthier) than patients identified pre-randomization, or more motivated for treatment, which could increase (or decrease) acute care utilization during the period after randomization. We are not powered to test for the difference in intervention effects between these two groups ( $\beta_1$ ); rather, the analyses proposed here are exploratory analyses that will generate hypotheses for testing in future studies.

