### Implications for PROUD Objective 2 Analyses

None of the tests considered performed uniformly well across all data generating scenarios considered, and the optimally performing test (i.e., with type 1 error rate closest to the nominal 0.05 level), varied highly depending on the scenario.

With the Objective 2 analysis clustered at the clinic level (see Section 5.3), the scenario that most closely aligns with our setting, based on PROUD Phase 1 data, is given in the top-right plot of the two Figures above. (For Phase 1, the ICC under a linear mixed model was approximately 0.02, average sample size within a cluster was approximately 100, and CV of cluster sizes was 1.2.)

For the results that align with the covariate adjustment setting under the primary analysis approach (Figure C1), the LRT with either BW1 or BW2 have reasonable type 1 error rates. For the results that align with the covariate adjustment setting under the secondary analysis approach (Figure C2), LRT with BW2 performs reasonably well (whereas with BW1 performance was overly conservative). We therefore selected LRT with BW2 (also referred to as “inner-outer”) for the testing approach that incorporates small sample methods.

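### The Objective 2 secondary-sample model has only a clinic intercept, so its omnibus test over-rejects if the new-versus-existing patient difference varies between clinics

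*SAP*

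**What the plan says.** SAP 5.5.3 takes the primary Objective 2 Poisson model, adds an indicator for patients first recognized after randomization (period) and its product with treatment, "and the other terms are defined as in the primary analysis", apart from the covariate list. The random part is therefore that of SAP 5.3: "The model will account for clustering of patients within a clinic by including clinic-specific random intercepts". No clinic-by-period term appears.

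The composite null β0 = β1 = 0 is tested against the alternative that at least one coefficient "is non-zero by conducting a likelihood ratio test". Effects are also estimated for existing patients (β0) and newly recognized patients (β0 + β1). Objective 2 shell Tables 4 and 5 each have a column for the omnibus P value.

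On small samples, SAP 5.3 says of trials with few clusters that "a small-sample correction is often necessary to obtain correct type 1 error rates", and reports that "using the likelihood ratio test with the Between-Within (BW) DF correction method" does generally well in the setting closest to this trial. Appendix C selects the LRT with BW2 "for the testing approach that incorporates small sample methods". Section 5.5.3 names no reference distribution and does not say whether that choice carries over.

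**The concern.** Treatment is constant within a clinic. The interaction β1 therefore compares six clinics with six on one quantity: the log rate in newly recognized patients minus the log rate in existing patients. The clinic intercept affects both groups equally and drops out of that difference. What remains as the yardstick is patient-level Poisson variation, which is very small in the large clinics. If clinics differ at all in how their new patients compare with their existing ones, for reasons unrelated to the intervention, the model reads that spread as evidence about treatment.

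At stake are the omnibus P value, the interval for β0 + β1, and the repeats of this model in SAP 5.5.4. The primary Objective 2 test is not affected, because its model has no period term.

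**Working it through.** **Inputs from the documents.** Clinic sizes (SAP 6.2.1): 9, 12, 63, 39, 58, 200, 100, 49, 27, 10, 388, 290, total 1,245. Mean acute-care days over two years: 4.0 × 2.04 = 8.16. Clinic SD τ = 0.23 (variance 0.055, SAP 5.3). Between-clinic df: 12 − 2 = 10. No separate alpha is given for the omnibus test, so the 0.05 of SAP 5.3 is carried over.

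**Assumed, because the documents are silent.** ω, the SD across clinics of the new-minus-existing log-rate difference, varied from 0 to 0.23. The ratio r of new to existing patients, varied from 0.25 to 2.

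**Step 1: reproduce the SAP's own error rates.** Maximum likelihood shrinks the clinic variance by 10/12, which inflates the Wald statistic by √1.2.
- Naive Wald: P(|t10| > 1.96/√1.2) = 0.104. SAP 6.2.2 states 0.104.
- Wald F with BW: P(|t10| > 2.228/√1.2) = 0.069. The SAP states 0.070.
- Simulation at τ = 0.23 (1,200 replicates): 0.112 and 0.073.

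**Step 2: see the mechanism in one clinic.** Clinic K1 expects 388 × 8.16 ≈ 3,166 days in existing patients. With r = 1, the Poisson variance of its new-minus-existing log ratio is 2/3,166 ≈ 0.00063, an SE of 0.025. If ω = 0.10, the true variance is 0.01 + 0.00063 ≈ 0.0106, about 17 times what the model allows. In the smallest clinic (9 × 8.16 ≈ 73 days) the Poisson variance is 2/73 ≈ 0.027, so ω = 0.10 adds little. The large clinics carry the weight: site K alone has (388 + 290)/1,245 = 54% of patients, with one clinic in each arm.

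**Step 3: simulate the planned test under β0 = β1 = 0.** The SAP model was fitted by Laplace maximum likelihood to clinic-by-period totals, with Poisson data, τ = 0.23 and 1,000-2,000 replicates per cell (Monte Carlo SE at most 1.6 points). Rejection rates for the LRT against chi-square(2):

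| r | ω = 0 | 0.05 | 0.10 | 0.15 | 0.23 |
|---|---|---|---|---|---|
| 0.25 | 8% | 18% | 34% | 48% | 65% |
| 0.5 | 7% | 22% | 44% | 60% | 70% |
| 1 | 8% | 26% | 52% | 65% | 77% |
| 2 | 8% | 33% | 57% | 67% | 81% |

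At ω = 0.03, run for r = 0.25 and 0.5 only, the rates are 10% and 12%. Changing τ to 0.12 or 0.35 at ω = 0.10 and r = 1 gives 50% in both cases.

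**Step 4: separate the two possible causes.** Keep the intercept-only model and refer LRT/2 to F(2,10). The error is 2-3% at ω = 0. With r = 1 it is 16%, 44%, 58% and 72% at ω = 0.05, 0.10, 0.15 and 0.23. Over r = 0.25-2 it is 25-50% at ω = 0.10 and 40-62% at ω = 0.15. The missing variance term is therefore the main cause, not the reference distribution.

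**Step 5: test the repair** (r = 1, 600 replicates per cell, clinic-by-period random effect added):

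| Reference | ω = 0 | 0.10 | 0.15 | 0.23 |
|---|---|---|---|---|
| chi-square(2) | 6.5% | 11.0% | 11.2% | 9.7% |
| F(2,10) | 1.7% | 4.8% | 3.3% | 3.7% |

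Both parts are needed.

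**Not simulated.** The demographic and neighborhood covariates, the 1.5-year follow-up at one health system, and the treatment-day outcome of shell Table 4.

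**The case against.** **The inflation rests on unknown inputs.** This stands. A reader might take a single figure, such as 50-70%, as a property of the planned test. The documents do not support that: they give neither ω nor the new-patient sample size, and at ω = 0 the error is only 7-8%. Only the conditional range can be defended.

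**SAP 5.5.1 does not establish clinic-to-clinic variation.** This also stands. It says newly recognized patients in intervention clinics "are likely to differ markedly from patients with newly recognized OUD in the UPC clinics post-randomization". A reader might take this as evidence for a non-zero ω, but it describes a systematic difference between arms, which is confounding. A random effect would not remove it.

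**The test may not be uncorrected.** SAP 5.5.3 calls its model similar to the primary one and names the same form of test as Appendix C. A reader might infer from its silence that no correction will be used, but the SAP does not say so. The point matters little, because F(2,10) alone leaves most of the inflation.

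**The analysis is exploratory.** SAP 5.5.3 says so and warns that β1 more likely reflects unmeasured confounders. The shells label these tables observational, and SAP 5.5.4.a adds a restriction to patients already in the health system. This limits the consequence. It does not answer the point: the warning concerns what β1 means, whereas the error rate here is wrong even when the arms do not differ systematically.

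**A second variance level lacks df guidance.** SAP 5.3 gives this reason for leaving out a health-system effect. It is a fair caution, and the 10 df come from a model with two fixed effects. The simulated 1.7-4.8% answers it for Poisson data only.

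**Conclusion.** The concern holds in conditional form. As specified, the 5.5.3 model makes no allowance for clinic-to-clinic variation in the difference between newly recognized and existing patients. With none, the omnibus test is mildly liberal (7-8% against chi-square). With assumed SDs of 0.05 up to the SAP's own clinic SD of 0.23, and size ratios of 0.25-2, its type I error is about 18-81%. Exactly zero variation is a strong assumption for a group formed by whom each clinic attracts and diagnoses, the more so because SAP 5.5.2 rules out adjusting for baseline acute care in the full secondary sample. That is a judgment, not something the documents show.

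The result assumes Poisson data and no covariates. Patient-level over-dispersion is a separate problem for the same test: with ω = 0, r = 1 and assumed variance-to-mean ratios of 2, 5, 10 and 20, the error is 16%, 36%, 47% and 63%. The change is worth making before the omnibus P values are reported, but no primary conclusion depends on it.

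**What to change.** In SAP 5.5.3:
- Add a clinic-by-period random effect to the model.
- State that the omnibus LRT uses the between-clinic (BW2-type) F reference, and give its denominator df.
- Use this model for the β0 and β0 + β1 intervals, the acute-care count measures in shell Table 5 and the repeats in 5.5.4. Use it also for the treatment-day count in shell Table 4, noting that its error rate there has not been checked.

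The cost is one variance parameter and a few sentences. Intervals widen, and the test is slightly conservative (about 2%) if there is no such variation. The change does not remove between-arm confounding of newly recognized patients or patient-level over-dispersion, and the exploratory label should stay.

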#### 5.5.4 Sensitivity Analyses of Primary Objective 2 Outcome Measure within the Objective 2 Secondary Sample

##### 5.5.4.a. Restricting to Patients in the HCS Pre-randomization

As discussed in Section 5.5.2, analyses in the full secondary sample that includes patients new to the HCS post-randomization are challenging due to the inability to adjust for baseline characteristics (including the baseline value of the outcome). To address this limitation, we plan to repeat the Objective 2 analysis in the secondary sample restricted to patients in the HCS pre-randomization (see Supplemental Figure Shell 1, Objective 2, Section 10.2) and using the full set of covariates as in the secondary analysis within the Objective 2 primary sample (described above in Section 5.4.1). Because differences in estimates in this sample could be due either to using a fuller set of covariate adjustment or using a different sample, we will additionally conduct this analysis using the same set of covariates as in Section 5.5.2 (age, gender, race/ethnicity, and neighborhood-level SES).

##### 5.5.4.b. Secondary Analyses Accounting for Implementation and Other Sensitivity Analyses

We also plan to apply the same set of sensitivity analyses in the Objective 2 secondary sample as in the Objective 2 primary sample, including among “active” patients (in the HCS, in PC; Section 5.4.2), among enrolled patients (in 2 HCSs; Section 5.4.3), under the alternate clinic assignment algorithm (Section 5.4.4), under modified analyses accounting for success of implementation (Section 5.4.5), and among patients with  $\geq 2$  OUD diagnoses (Section 5.4.6) over the full study period.

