#### 3.4 Objective 2 Secondary Study Sample

The Objective 2 primary sample as defined in the preceding section, which restricts analyses to patients seen in PROUD trial clinics with documented OUD pre-randomization, was selected for primary analyses to avoid the potential for *identification bias* (type of selection bias that can occur when the analytic sample is defined using post-randomization data). However, an important limitation of analyses within the Objective 2 primary sample is that they miss any impact of the PROUD intervention among patients with a new OUD diagnosis post-randomization, including patients who initiate treatment in PROUD intervention clinics who are diagnosed with OUDs after randomization, and patients who are newly attracted to the clinic specifically because of the PROUD intervention. To address this limitation, secondary analyses are conducted in a broader sample that includes patients new to the PROUD trial clinics or with newly recognized OUDs post-randomization (see Figure Shell 1, Objective 2 paper, Section 10.2).

Specifically, the effectiveness (Objective 2) secondary study sample is defined as the subset of patients from the main trial sample who had a documented OUD diagnosis during either the pre-

randomization or follow-up periods and who were age  $\geq 16$  as of the start of the baseline period. Clinic assignment for the Objective 2 secondary sample will be the same as above.

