## 4.0 OUTCOME MEASURES

### 4.1 Definition of Primary Implementation Outcome Measure

The primary outcome (clinic-level measure) is the number of patient days of OUD medication treatment documented in the EHR in each clinic post-randomization. To account for varying clinic sizes, the clinic-level outcome is divided by the number of patients seen in the clinic post-randomization and then multiplied by an appropriate scaling factor in order to report the results (e.g., multiplying by 10,000 to calculate the number of patient days of OUD treatment per 10,000 patients), and reported as patient-years of treatment provided by a clinic (calculated by simply dividing days of OUD treatment by 365).

“OUD medication treatment” includes medications for OUD that can be prescribed in PC and documented in EHRs—buprenorphine formulations indicated for OUD (oral, implants, sustained release injection with or without an OUD diagnosis) or injectable extended release (XR) naltrexone with a diagnosis of OUD. An OUD diagnosis is required for injectable XR naltrexone because it is often used for alcohol use disorders (AUD). We do not require an OUD diagnosis for buprenorphine because there are buprenorphine formulations specific for OUD and PROUD Phase 1 analyses revealed OUD diagnoses are often missing, consistent with the literature. Further, an OUD diagnosis is likely to be documented by PROUD clinic providers based on the PROUD NCM manual, so that requiring an OUD diagnosis could bias findings toward favoring the intervention clinics.

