#### **5.4.6 Objective 2 Sensitivity Analysis Applying Stricter Eligibility Criteria**

Our primary analysis requires just a single OUD diagnosis pre-randomization for a patient to be included in the sample, as well as just a PC visit at any time pre-randomization (up to 3 years). To account for the possibility that having only one diagnosis could reflect an error in identifying OUD and that patients with a PC visit early in the pre-randomization period may have left the clinic, we will conduct a sensitivity analysis among the sub-sample of our primary sample that restricts to patients with both  $\geq 2$  days with an OUD diagnosis during the pre-randomization period and a PC visit in the year prior to randomization.

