## 10.2 Objective 2 Paper

**Figure 1.** Cohort identification of patients for the primary and larger secondary sample of the PROUD Trial effectiveness analyses

**Supplemental Figure 1.** Samples of patients in the primary and secondary Objective 2 analysis

HCS = health care system

rand. = randomization

\* OUD diagnosis anywhere in the health system

\*\* Defined by having any visit, diagnosis, or procedure

**Table 1.** Characteristics of primary care patients with documented OUD who visited PROUD trial clinics (Effectiveness Objective Samples)

Characteristic	Pre-randomization Sample: Patients in Trial Clinics with Documented OUD Pre-randomization		Post-randomization Sample a, b : Patients New to Trial Clinics or with Newly Documented OUD Post-randomization	
	Intervention	Usual Care	Intervention	Usual Care
	(N = )	(N = )	(N = )	(N = )
	%			
Age at randomization, years				
16-17				
18-24				
25-44				
45-64				
65-74				
75+				
Female				
Race/ethnicity				
Hispanic ethnicity				
Non-Hispanic				
Asian				
Black or African American				
American Indian / Alaska Native				
Native Hawaiian or Pacific				
Islander				
White				
Multiple race				
Other race				
Missing race and ethnicity data				

**Table 1.** Characteristics of primary care patients with documented OUD who visited PROUD trial clinics (Effectiveness Objective Samples)

Characteristic	Pre-randomization Sample: Patients in Trial Clinics with Documented OUD Pre-randomization		Post-randomization Sample a, b : Patients New to Trial Clinics or with Newly Documented OUD Post-randomization	
	Intervention (N = )	Usual Care (N = )	Intervention (N = )	Usual Care (N = )
Insurance status closest to randomization b				
Medicare				
Medicaid				
Otherwise insured (e.g., commercial, private)				
Uninsured				
Unknown				
Unstable housing including homelessness b				
Socioeconomic status variables using zip code closest to randomization, median (IQR)				
Median household income				
% unemployed				
% below federal poverty level				
Comorbidity in the two years pre-randomization b				
Alcohol use disorder				
Other (non-opioid) substance use disorder				
Schizophrenia and other psychotic disorders				

**Table 1.** Characteristics of primary care patients with documented OUD who visited PROUD trial clinics (Effectiveness Objective Samples)

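### SAP 5.5.4.b screens the pre-randomization stratum on OUD codes recorded during follow-up, adding avoidable arm-dependent selection of unknown direction to that stratum's effect estimate (β₀)

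*SAP*

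**What the plan says.** SAP 5.4.6 restricts the Objective 2 primary sample to patients with at least two "days with an OUD diagnosis during the pre-randomization period and a PC visit in the year prior to randomization". Its stated reasons are that a single code may be an error and that a patient seen early in the three-year window may have left the clinic.

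SAP 5.5.4.b repeats the Objective 2 sensitivity analyses in the secondary sample. For this check it requires at least two "OUD diagnoses (Section 5.4.6) over the full study period". It does not say whether the visit condition still applies, and it speaks of diagnoses where 5.4.6 speaks of days.

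Four other places bear on this:

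- SAP 3.4 rests the primary sample on avoiding identification bias, described as a "type of selection bias that can occur when the analytic sample is defined using post-randomization data".
- SAP 4.1 says that "an OUD diagnosis is likely to be documented by PROUD clinic providers based on the PROUD NCM manual".
- A footnote to the sample figure in SAP 10.2 counts an "OUD diagnosis anywhere in the health system". No exclusion of ED, urgent-care or inpatient codes is given.
- SAP 5.5.3 estimates the effect separately in the pre-randomization stratum (β₀) and the post-randomization stratum (β₀ + β₁). Table shells 4 and 5 give each its own columns.

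**The concern.** Under SAP 3.3 and 3.4.1 a patient belongs to the pre-randomization stratum on pre-randomization data alone, so β₀ compares groups that the intervention could not have shaped. The full-period count removes that protection inside this check. A patient with a single earlier code stays only if a second code appears, and that code may be written during follow-up. It can come from nurse and prescriber visits, which differ by arm, or from acute-care encounters, which are the outcome. Retention then depends on arm and outcome together.

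The check exists to show whether miscoding matters. If arm-dependent coding can also move the estimate, a shift from the unrestricted result cannot be attributed to miscoding. The model offers no correction: SAP 5.5.2 explains that analyses including patients new to the health system cannot adjust for baseline acute care. The same section prefers pre-randomization values where they exist, and for this stratum they do.

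**Working it through.** **The plan's figure.** The SAP gives no figure for this check. Its Objective 2 outcome mean (SAP 6.2.1) is 4.0 acute-care visits × 2.04 days = 8.16 days over two years, and log(8.16) = 2.10, as stated. With days proportional to visits, 2.04 cancels from a ratio, so visits V with mean 4 suffice.

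**Assumptions, none from the documents.**

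- s: share of the stratum already holding two pre-randomization codes, 0.5–0.8.
- q: chance that an acute visit generates an OUD code, 0.05–0.40.
- d: chance of a second code from other care during follow-up, 0.3 in UPC and 0.5–0.8 in PROUD.
- V: Poisson, or gamma-Poisson with shape k = 2, 1 or 0.5, identical in both arms (no true effect).

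**Formula.** A single-code patient is kept with probability 1 − (1 − d)(1 − q)^V. For gamma-Poisson V, let b = 1 + 4q/k. Then

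- A = E[(1 − q)^V] = b^(−k)
- B = E[V(1 − q)^V] = 4(1 − q)·b^(−k−1)
- fraction kept = s + (1 − s)[1 − (1 − d)A]
- mean visits among the kept = {4s + (1 − s)[4 − (1 − d)B]} / fraction kept

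**Case 1: extra documentation unrelated to severity.** k = 1, s = 0.5, q = 0.20, d = 0.3 (UPC) and 0.8 (PROUD). Here b = 1.8, A = 0.5556, B = 0.9877.

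- UPC: kept 0.5 + 0.5(1 − 0.7 × 0.5556) = 0.806; mean (2 + 0.5 × 3.309)/0.806 = 4.536.
- PROUD: kept 0.5 + 0.5(1 − 0.2 × 0.5556) = 0.944; mean (2 + 0.5 × 3.802)/0.944 = 4.131.
- Null RR = 4.131/4.536 = 0.91.

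Over the whole grid the RR runs from 0.877 (k = 0.5, s = 0.5, q = 0.20, d = 0.3 against 0.8) to 0.998 (Poisson, s = 0.8, q = 0.05, d = 0.3 against 0.5), that is 0.88–1.00. It is exactly 1.00 if d is equal in both arms, or if q = 0.

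**Case 2: extra documentation follows acute care.** SAP 5.5.1 itself notes that "patients could be referred for ongoing buprenorphine treatment from an ED or hospital that started treatment". Keep k = 1, s = 0.5 and d = 0.3 in both arms. Let q = 0.05 in UPC, and let each PROUD acute visit carry a further 0.10 chance of a referral code: q = 1 − 0.95 × 0.90 = 0.145.

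- UPC: A = 0.8333, B = 2.639; kept 0.708; mean 4.343.
- PROUD: b = 1.58, A = 0.6329, B = 1.370; kept 0.778; mean 4.522.
- Null RR = 4.522/4.343 = 1.04.

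Starting from q = 0.20 instead, the same extra gives 1.00. Simulation with documentation tied more steeply to acute-care use gave 1.00–1.08.

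**Pre-randomization count.** Retention does not depend on follow-up, so the mean is 4s/s = 4 in both arms and RR = 1.00. Simulation gave 0.996–1.004, which is Monte Carlo noise.

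These are crude ratios of means, not fits of the planned mixed model, and the visit condition is not modelled.

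**The case against.** The strongest reply is that the wider window follows from the sample. SAP 3.4 says that "secondary analyses are conducted in a broader sample that includes patients new to the PROUD trial clinics or with newly recognized OUDs post-randomization", and most patients first coded after randomization could never meet a pre-randomization rule. The parent sample already selects on one follow-up code. The SAP acknowledges that bias, calls these analyses exploratory, and titles the table shells observational. The clean check also survives: 5.4.6 still applies to the primary sample, which contains the same patients as this stratum.

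For the post-randomization sample most of this stands. Under severity-independent documentation the null RR there was 0.66–0.99 with the two-code check, but already 0.72–0.98 with the parent one-code rule. At q = 0.05 the check can be the less biased of the two (for example 0.94 against 0.89). That distortion is not specific to this check.

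For β₀ the reply fails. In the parent sample this stratum carries no post-randomization selection; the full-period count introduces it, although every patient there can be screened on earlier codes. An exploratory label does not justify an avoidable bias.

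A reader might go further and infer that the check will show a reduction where none exists. The documents do not support that. It needs both severity-independent extra documentation in PROUD and OUD codes arising from acute visits, and the SAP gives a rate for neither. The referral route in 5.5.1 can cancel or reverse the sign, and 5.5.3 leaves open whether new patients are sicker or healthier.

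**Conclusion.** The point holds for the pre-randomization stratum. As written, 5.5.4.b lets follow-up codes decide who contributes to β₀, contrary to the SAP's own reason for its primary sample. With no true effect the distortion is about 0.88–1.00 under severity-independent documentation and about 1.00–1.08 under severity-linked documentation. Both ranges rest on assumed code rates, so size and direction are unknown in advance.

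The scope is narrow: one sensitivity analysis in an exploratory sample. The composite test in that analysis also uses β₀, so it is touched too. Notes to table shells 4 and 5 say the pre-randomization columns will probably be left out of the main paper, which limits the exposure further. The primary Objective 2 analysis and the 5.4.6 check in the primary sample are unaffected.

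**What to change.** In SAP 5.5.4.b:

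1. For the pre-randomization stratum, apply 5.4.6 unchanged: at least two OUD-diagnosis days and a primary care visit in the prior year, all before randomization.
2. For the post-randomization sample, keep the full-period count and state that this part is selected on post-randomization data.
3. Optionally, add a version for that sample that does not count codes from ED, urgent-care or inpatient records. This removes the acute-care coding route, but not documentation that itself tracks severity.

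The cost is a sentence or two. The two strata would then use different look-back windows, and fewer pre-randomization patients would be kept: in case 1, 50% in each arm instead of 81% in UPC and 94% in PROUD, before the visit condition.
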